3. OBJECTIVES AND ENDPOINTS

Objectives	Endpoints
Primary	
To evaluate the clinical response of sirukumab (administered as a single IV dose) + SOC compared to placebo + SOC in confirmed critical COVID-19 disease	
 • Time to improvement^a of at least 2 categories relative to Baseline on the 6-point ordinal clinical recovery scale (up to Day 28)
Key secondary	
To evaluate the clinical response of sirukumab + SOC compared to placebo + SOC in confirmed critical COVID-19 disease	
 • Proportion of participants with an improvement on Day 28 of at least 2 categories relative to Baseline on the 6-point ordinal clinical recovery scale • Incidence of all-cause mortality (up to Day 28)
Other Secondary	
To evaluate the clinical response of sirukumab (administered as a single IV dose) + SOC compared to placebo + SOC in confirmed severe or critical COVID-19 disease	
 • Time to improvement^a of at least 2 categories relative to Baseline on the 6-point ordinal clinical recovery scale (up to Day 28)
To evaluate the clinical response of sirukumab + SOC compared to placebo + SOC in confirmed severe or critical COVID-19 disease	
 • Proportion of participants with an improvement on Day 28 of at least 2 categories relative to Baseline on the 6-point ordinal clinical recovery scale • Incidence of all-cause mortality (up to Day 28)
To evaluate the safety of sirukumab + SOC compared to placebo + SOC in confirmed (a) critical and (b) severe or critical COVID-19 disease	
 • Incidence of SAEs (up to Day 28) • Incidence of related AEs (up to Day 28) • Proportion of participants with severe or life-threatening bacterial, invasive fungal, viral or opportunistic infections (other than SARS-CoV-2) (up to Day 28) • Incidence of grade 3 and 4 neutropenia and lymphocytopenia (up to Day 28) • Incidence of increased ALT $\geq 3 \times$ULN combined with increased bilirubin $> 2 \times$ULN (up to Day 28)

^aThe improvement should be sustained until Day 28 (or discharge/discontinuation).

Objectives	Endpoints
To evaluate the clinical response of sirukumab + SOC compared to placebo + SOC in confirmed (a) critical and (b) severe or critical COVID-19 disease	
 Time to improvement^a of at least 1 category relative to Baseline on the 6-point ordinal clinical recovery scale (up to Day 28) Proportion of participants with an improvement on Day 28 of at least 1 category relative to Baseline on the 6-point ordinal clinical recovery scale Time from study intervention to end of oxygen supplementation (up to Day 28) Time from study intervention to hospital discharge among the surviving participants (up to Day 28) Total length of hospitalization among the surviving participants (up to Day 28) Number of ventilation free days (up to Day 28) Participant's clinical status at Day 7, 14, 21, 28 (6-point ordinal clinical recovery scale) Total time on invasive mechanical ventilation Proportion of participants with a worse^b category relative to Baseline on the 6-point ordinal clinical recovery scale (up to Day 28) Proportion of participants on extracorporeal membrane oxygenation (ECMO) over time Total time on ECMO
To evaluate the safety during follow-up for (a) critical and (b) severe or critical COVID-19 disease	
 Proportion of alive participants at Day 28, Week 8, and Week 16 Proportion of alive participants that required readmission at Week 8 and Week 16 (if previously discharged) Incidence of SAEs up to Week 16
Exploratory	
To evaluate biomarkers that may be associated with response to or complications of sirukumab treatment	Evaluations may include, but are not limited to, IL-6, procalcitonin, C-Reactive protein (CRP), ferritin, LDH and D-dimer serum concentrations (through Day 28)
To explore changes in SARS-CoV-2 viral load and viral genome	
 Time to SARS-CoV-2 undetectable viral load by RT-PCR (up to Day 28) SARS-CoV-2 viral load over time by RT-PCR (up to Day 28)

^a The improvement should be sustained until Day 28 (or discharge/discontinuation).^b Clinical recovery scale score worsened with at least 1 category between Day 5 and Day 28.

Objectives	Endpoints
	
 Proportion of participants with undetectable viral load (at multiple time points up to Day 28) Development of SARS-CoV-2 variants
To evaluate the incidence of SARS-CoV-2 viremia	
 Proportion of participants with SARS-CoV-2 viremia (at multiple time points up to Day 28)
To evaluate pharmacokinetics following sirukumab 5 mg/kg treatment	
 Sirukumab serum concentrations
To evaluate immunogenicity following sirukumab treatment	
 Proportion of participants with sirukumab antibodies (Day 28 or at discharge if discharged after Day 28)
To evaluate SARS-CoV-2 humoral immunity	
 Serum levels of SARS-CoV-2 specific antibodies

Refer to Section 8, Study Assessments and Procedures for evaluations related to endpoints.

At the time of data analysis, additional endpoints may be considered for analysis in function of the evolution in scientific knowledge on COVID-19.

HYPOTHESIS

The primary hypothesis of this study is that sirukumab in combination with SOC results in a statistically significant shorter time to improvement (defined as an improvement of at least 2 categories relative to Baseline on the 6-point ordinal clinical recovery scale) versus placebo in combination with SOC, in participants with confirmed critical COVID-19 disease.

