Self-reported oxygen needed (yes/no)					X ⁿ	X ⁿ		
Self-reported pregnancy status					X ⁿ	X ⁿ		
Record readmission(s) post discharge and reason					X ⁿ	X ⁿ		

- Laboratory testing to be performed centrally

Note: If multiple assessments are scheduled for the same timepoint, it is recommended that procedures be performed in the following sequence: ECG, oxygen saturation, vital signs, blood sampling.

Abbreviations: AE: adverse event, AESI: adverse event of special interest; aPPT: activated partial thromboplastin time; CRP: C-reactive protein; CT: computed tomography; DBP: diastolic blood pressure; FiO₂: percentage of inspired oxygen; ECG: electrocardiogram; HDL: low-density lipoprotein; ICF: informed consent form; ICU: intensive care unit; INR: international normalized ratio; LDL: low-density lipoprotein; PaCO₂: partial pressure of carbon dioxide in arterial blood; PaO₂: partial pressures of oxygen in arterial blood; PCR: polymerase chain reaction; PT: prothrombin time; SAE: serious adverse event; SBP: systolic blood pressure; SOC: standard of care; SpO₂: peripheral capillary oxygen saturation.

Footnotes:

- a. Screening assessments start after signing of the ICF and can continue on the next calendar day, if needed. All screening and baseline assessments may also take place on the same day. Screening/Baseline assessments required to verify study eligibility and data collection for assessment of the 6-point ordinal clinical recovery category should take place prior to randomization. All Screening/Baseline procedures should take place prior to study drug administration.
- b. The assessment schedule will be on a weekly basis for participants still hospitalized after Day 28. For the required assessments, refer to Section [10.3, Appendix 3: Clinical and Laboratory Assessments Described per Day](#).
- c. Consent to be obtained before the first study-related activity. An exception is in the case of an emergency enrollment in which the informed consent can be obtained as soon as possible.
- d. If a participant's clinical status changes after screening but before randomization such that he or she no longer meets all eligibility criteria, then the participant should be excluded from participation in the study.
- e. Medical history should include collecting onset of COVID-19 symptoms, prior therapy, and date of SARS-CoV-2 diagnosis if available.
- f. A urine pregnancy test is to be performed in women of childbearing potential only.

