 - General safety chemistry: total protein, albumin, aspartate aminotransferase (AST), alanine aminotransferase (ALT), alkaline phosphatase (ALP), total bilirubin, glucose, sodium, potassium, calcium, phosphate, magnesium, chloride, bicarbonate, creatinine, blood urea nitrogen (BUN), creatine phosphokinase (CPK), lactate dehydrogenase (LDH), lactate, and troponin. If ALT or AST >3x ULN or 3x the entry level (if entry levels were >ULN), also provide conjugated bilirubin (direct), unconjugated bilirubin (indirect).
- m. Culture results (bacterial, fungal, or viral) including site of infection and specimen source (bronchoalveolar lavage [BAL], tracheal aspirate, sputum, blood, urine, etc.), performed as part of patients' workup for new infections, should be reported. Analyses will be performed by the local laboratory.
- n. For participants discharged or who discontinued the study prior to Day 28 and did not withdraw consent, phone calls will be conducted on Day 28 and during the post Day 28 Follow-up Phase to record concomitant medication, the vital status, the occurrence of AEs, self-reported oxygen need, self-reported pregnancy status and the history of readmission since last contact.
- o. Whenever possible, vital status will be recorded if the patient is alive. If the participant is deceased, date and cause of mortality should be recorded in the eCRF. Death should be documented as SAE.
- p. NP swabs will be used to collect secretions from participants to explore quantification of viral load of SARS-CoV-2. For each participant, NP sampling should be done at approximately the same time (± 4 hours) on each sampling day and from the same nostril.
- q. If an NP sample for detection of SARS-CoV-2 (local SOC) will be collected on the same day as the NP sample for quantification of SARS-CoV-2 (central lab), only one NP sample should be collected. The sample should be aliquoted and the remaining aliquots of the NP samples should be stored and sent to the central lab for quantification of SARS-CoV-2.
- r. SARS-CoV-2 positivity should be documented based on local testing on any specimen, by RT-PCR, any time before randomization. This might require a local test using an NP swab obtained at screening.
- s. After randomization, SARS-CoV-2 positivity will be confirmed in a central lab by quantitative RT-PCR. The baseline sample needs to be collected predose, as close as possible to dosing.

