8.2.6. Vital Status

At Day 28 (if discharged before Day 28), and during the post Day 28 follow-up phase (phone call visits), vital status of study participants will be recorded, if the participant is alive. If the participant is deceased, date and cause of mortality should be recorded. Death should be documented as SAE in the eCRF.

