8.3.6. Adverse Events of Special Interest

Adverse events of special interest for the single IV administration of sirukumab (5 mg/kg) are provided below.

Table 2: Events of Interest for a Single IV Dose of Interest

Potential Risks of Clinical Significance	Summary of Data/ Rationale for Risk	Mitigation Strategy
Serious infections (Bacterial, fungal, and viral infection)	Interleukin-6 stimulates hepatic acute-phase proteins and Ig production and promotes the growth and differentiation of T cells, B cells, and tumor cells. Interleukin-6 is a mediator of inflammation and cellular immune responses in the defense against some intracellular pathogens. Interleukin-6 has been known to serve as a marker of disease severity for infections. Although IL-6 modulates certain physiologic acute-phase responses to infection, a complete lack of IL-6 has not been shown to alter mortality rates in IL-6 knockout mice. Blockage of IL-6 may blunt the acute-phase pyretic response and therefore, fever may be masked in participants receiving sirukumab. Serious, life-threatening infections such as septic shock, some of which have been fatal, have occurred in participants receiving sirukumab.	Inclusion and exclusion criteria; hematologic monitoring; safety evaluation; and supportive treatment.
Hypersensitivity	Reactions observed in humans after IV or SC administration of mAbs include headache, fever, facial flushing, pruritus, urticaria, dermatitis, myalgia, nausea, chest tightness, laryngeal edema, dyspnea, vomiting, erythema, abdominal discomfort, diaphoresis, shivers, hypertension, Stevens-Johnson syndrome, lightheadedness, hypotension, palpitations, and somnolence.	Inclusion and exclusion criteria; clinical monitoring; safety evaluation; and supportive treatment.
Hematologic Events	Neutropenia and thrombocytopenia have occurred in sirukumab studies, including severe thrombocytopenia associated with bleeding. In the Phase 2 and Phase 3 RA studies, decreases in ANC and platelets occurred in all sirukumab treatment groups. Most patients who developed neutropenia while being treated with sirukumab did not	Inclusion and exclusion criteria; clinical monitoring; safety evaluation; and supportive treatment.

	develop infections, and most patients who developed thrombocytopenia did not report bleeding events. Changes were not observed in participants who received placebo, but did occur after participants crossed over to active treatment. No dose response was observed.	

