10.5.5. Procedures

All Adverse Events

Adverse events, collected as specified in Section 8.3.1, must be recorded using medical terminology in the source document and the eCRF. Whenever possible, diagnoses should be given when signs and symptoms are due to a common etiology (eg, cough, runny nose, sneezing, sore throat, and head congestion should be reported as "upper respiratory infection"). Investigators must record in the eCRF their opinion concerning the relationship of the adverse event to study therapy. All measures required for adverse event management must be recorded in the source document and reported according to sponsor instructions.

The participant, once discharged, will be provided with a "wallet (study) card" and instructed to carry this card with them for the duration of the study indicating the following:

- Study number
- Statement, in the local language(s), that the participant is participating in a clinical study
- Investigator's name and 24-hour contact telephone number
- Local sponsor's name and 24-hour contact telephone number (for medical personnel only)
- Site number
- Participant number
- Any other information that is required to do an emergency breaking of the blind

Serious Adverse Events

All serious adverse events that have not resolved by the end of the study, or that have not resolved upon the participant's discontinuation from the study, must be followed until any of the following occurs:

- The event resolves
- The event stabilizes
- The event returns to baseline, if a baseline value/status is available
- The event can be attributed to agents other than the study intervention or to factors unrelated to study conduct
- It becomes unlikely that any additional information can be obtained (participant or health care practitioner refusal to provide additional information, lost to follow-up after demonstration of due diligence with follow-up efforts)

Any event requiring hospitalization (or prolongation of hospitalization) that occurs during participation in the study must be reported as a serious adverse event.

The cause of death of a participant in a study, whether or not the event is expected or associated with the study intervention, is considered a serious adverse event.

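### The follow-up readmission endpoint counts only participants still alive, so it drops readmissions that end in death and can dilute or, in some cases, reverse the arm comparison

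*Protocol*

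**What the plan says.** Under the objective on safety during follow-up, protocol Section 3 lists three endpoints:

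- The first concerns survival and is worded "Proportion of alive participants at Day 28, Week 8, and Week 16".
- The second, which is at issue here, concerns readmission and is worded "Proportion of alive participants that required readmission at Week 8 and Week 16 (if previously discharged").
- The third concerns serious events, with no restriction to survivors, and is worded "Incidence of SAEs up to Week 16".

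The protocol synopsis and SAP 1.1 carry the same three. The SAP does not develop the readmission endpoint further. It is absent from the derivation tables in SAP 5.4.1 and from the safety methods in SAP Section 9. The full-analysis-set denominator in SAP 5.4.2 applies to the incidence parameters defined in 5.4.1, and readmission is not one of them. Nothing says how a readmission followed by death is counted, or whether the endpoint means any readmission up to the visit or status at the visit.

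On data collection, the Schedule of Activities has a line for the phone calls, "Record readmission(s) post discharge and reason", and its footnote n asks for "self-reported pregnancy status and the history of readmission since last contact". Protocol 10.5.5 states: "Any event requiring hospitalization (or prolongation of hospitalization) that occurs during participation in the study must be reported as a serious adverse event". Protocol 8.2.6 adds: "Death should be documented as SAE in the eCRF".

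**The concern.** Being alive at Week 8 or Week 16 is an outcome that treatment may affect. Restricting a readmission rate to those alive removes, by definition, the readmissions that ended worst. It also removes more of them from whichever arm has more.

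Protocol 2.2 expects IL-6 suppression to last at least 4 weeks after the single dose, which can extend beyond discharge. Protocol 8.3.6 notes: "Serious, life-threatening infections such as septic shock, some of which have been fatal, have occurred in participants receiving sirukumab". A fatal infectious readmission is therefore an event a reader would expect a readmission endpoint to count. If such events differed between arms, the tabulated readmission comparison could understate the difference or point the wrong way.

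**Working it through.** The plan gives no rate, power or sample size for this endpoint, so there is no figure to reproduce. The check is algebraic, followed by assumed counts.

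**Notation, per arm.** n = discharged alive; r = readmitted by the time point; f = readmitted and dead by then; o = dead by then without readmission.

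- All readmissions: r/n.
- Endpoint as worded: (r − f)/(n − f − o).

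**Within an arm.** With o = 0, (r − f)/(n − f) < r/n whenever f > 0 and r < n. This was also confirmed for every n from 5 to 100, r from 1 to n − 1 and f from 1 to r. With o > 0, cross-multiplying gives understatement if and only if f(n − r) > r·o.

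Deaths without readmission act the other way. With assumed n = 52, r = 8, f = 0 and o = 5, the endpoint is 8/47 = 17.0%, against 8/52 = 15.4%.

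**Between arms.** Counts below are assumptions, per 100 discharged in each arm, with o = 0.

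| Case | Sirukumab: non-fatal + fatal | Placebo: non-fatal + fatal | All readmissions | Endpoint as worded |
|---|---|---|---|---|
| A | 10 + 10 | 18 + 2 | 20% vs 20% | 10/90 = 11.1% vs 18/98 = 18.4% |
| B | 10 + 15 | 18 + 2 | 25% vs 20% | 10/85 = 11.8% vs 18/98 = 18.4% |
| C | 18 + 10 | 18 + 2 | 28% vs 20% | 18/90 = 20.0% vs 18/98 = 18.4% |
| D | 10 + 15 | 10 + 0 | 25% vs 10% | 10/85 = 11.8% vs 10/100 = 10.0% |

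In A and B, fatal readmissions take the place of non-fatal ones. The arm with more fatal readmissions looks better, and in B the true order is reversed. In C and D they come on top of an equal non-fatal count. The order is kept, but the gap shrinks from 8 points to 1.6 in C and from 15 to 1.8 in D.

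**At about the planned size.** Protocol 9.2 plans 74 and 37 critical participants with 20% and 40% Day 28 mortality. That leaves 74 × 0.80 ≈ 59 and 37 × 0.60 ≈ 22 survivors, all assumed discharged. Readmission counts are again assumed.

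- 6 + 6 versus 4 + 0: all readmissions 12/59 = 20.3% vs 4/22 = 18.2%; endpoint 6/53 = 11.3% vs 18.2% (reversed).
- 11 + 6 versus 4 + 0: all readmissions 17/59 = 28.8% vs 18.2%; endpoint 11/53 = 20.8% vs 18.2% (diluted).

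**The case against.** The strongest reply is that nothing is hidden. The same objective reports survival at the same time points and SAEs to Week 16 with no restriction to survivors. A hospitalisation is an SAE and so is a death. SAP 9.1.3 tabulates serious events, events of special interest (which include serious infections) and events leading to death for both the treatment and follow-up phases. A fatal septic readmission would appear in all of these. This stands, and it limits the consequence.

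It does not restore the readmission rate:

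- The SAE tables are organised by MedDRA term and phase, over all treated participants rather than those discharged.
- SAP 2.1.1 starts the follow-up phase after Day 28, so readmissions before and after that day fall in separate tables, mixed with events in participants never discharged.

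A reader might infer that an excess of fatal readmissions will always look like fewer readmissions, or that the comparison always favours the arm with more deaths after discharge. The documents support neither. Cases C and D keep the order, and deaths without readmission raise the proportion. Nor do the documents support a particular size. They give no readmission or post-readmission fatality rate, and they attribute the known risks largely to chronic repeat dosing (protocol 2.3.3). In the lupus nephritis study, all serious infections followed at least 4 doses (protocol 2.1.1).

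It can also be said that alive was meant as discharged alive. No text says so, and the companion survival endpoint uses the word for status at the visit.

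Finally, footnote o of the Schedule of Activities names only date and cause for a deceased participant. Readmission history for someone who died may have to come from SAE records. That is a fair point and is allowed for in the fix.

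**Conclusion.** The concern holds in a limited form. As worded, the endpoint conditions on survival. Where there are no other deaths, it understates readmissions in any arm that has fatal ones. Deaths without readmission pull the other way, so the net bias depends on the mix of deaths. The arm comparison can be diluted or, in some scenarios, reversed. How much cannot be known from the documents: every readmission count above is an assumption, and the planned-size example also assumes that all Day 28 survivors are discharged.

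The damage is confined to one descriptive secondary safety endpoint outside the primary and key secondary testing hierarchy. No alpha, power or primary result changes. It is still worth correcting, because a stated rule removes the readmissions of most interest and no planned table gives the rate among those discharged.

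**What to change.** In protocol Section 3 (and the matching synopsis line) and SAP 1.1, with a derivation in SAP 5.4:

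1. Denominator: all participants discharged alive.
2. Numerator: any readmission by Week 8, and by Week 16, whatever the later vital status. Use the phone-call records, and the hospitalisation SAE records for participants who died. Saying *by* rather than *at* also settles whether the endpoint is cumulative.
3. Add one row by arm for readmission or death after discharge.

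SAP 5.4.1 already does something similar for time to hospital discharge, where it sets an all-participant version beside the version limited to survivors.

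The cost is revised wording, one extra table row and some use of SAE records for deceased participants. A competing-risk analysis (death without readmission as the competing event) and a second version over all treated participants are optional.

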4. STUDY DESIGN

4.1. Overall Design

This is a randomized, double-blind, placebo-controlled, multicenter, interventional Phase 2 study in hospitalized participants with confirmed COVID-19 disease, at risk for progressing to severe ARDS.

Up to protocol amendment 4, a target of approximately 270 participants with confirmed severe or critical COVID-19 disease was randomly assigned in a 2:1 ratio to receive 1 of the following 2 treatments:

- Treatment Arm: sirukumab 5 mg/kg IV single dose infusion on Day 1 + SOC treatment
- Control Arm: placebo IV single dose infusion on Day 1 + SOC treatment

More information on the SOC treatment is provided in Section 6.8 Prestudy and Concomitant Therapy.

As of protocol amendment 5, the study aims to enroll approximately 111 participants with confirmed critical COVID-19 disease overall in the study. The primary and key secondary analyses will be tested on the participants with confirmed critical COVID-19 disease.

At the time of release of protocol amendment 5, approximately 100 participants with confirmed severe COVID-19 disease had been enrolled. The overall population of participants with confirmed severe or critical COVID-19 disease will be analyzed as part of secondary objectives of the study.

Randomization is stratified by age (<65 and \geq 65 years of age) and by use of invasive mechanical ventilation (yes/no) at the time of randomization.

The study will include a Screening Phase, a 'Day 1 to Day 28' Phase and Post Day 28 Follow-up Phase (phone calls on Week 8, Week 12 and Week 16). The entire study duration for each participant will be 16 weeks with daily study assessments up to Day 28 or day of discharge (whichever comes first), and phone call assessments thereafter, ie, at Day 28 in case of discharge prior to Day 28, at Week 8, 12 and 16. The assessment schedule will be on a weekly basis for participants still hospitalized after Day 28. The study is considered completed with the completion of the last study assessment (phone call assessment at Week 16) for the last participant in the study or the discontinuation of the last participant in the study, whichever comes last. For details, refer to the [Schedule of Activities \(SoA\)](#).

The impact of a single dose treatment with sirukumab on Day 1 + SOC on confirmed critical COVID-19 disease will be evaluated throughout the study. Refer to the [Schedule of Activities \(SoA\)](#) and Section 8, Study Assessments and Procedures for details.

The primary endpoint is the time to improvement of at least 2 categories relative to Baseline on the 6-point ordinal clinical recovery scale (up to 28 days). The improvement should be sustained until Day 28 (or discharge/discontinuation). For details, refer to Section 8.1.1, Six-point Ordinal Clinical Recovery Scale.

The primary analysis will be done when all participants reached Day 28 or discontinued earlier.

The final analysis will be done when all participants completed the study.

The DMC reviewed the interim data after the first 30 participants with confirmed severe or critical COVID-19 disease had been dosed and have had at least 7 days of follow-up after study intervention. Details regarding the DMC are provided in Committees Structure in Section 10.4.6.

A non-binding unblinded IA for futility was performed by the sponsor on the primary endpoint when approximately 20% of the planned number of participants with confirmed severe or critical COVID-19 disease had reached Day 28 or discontinued earlier. Additional IAs on participants with confirmed critical COVID-19 disease are not planned for the study.

A diagram of the study design is provided in Section 1.2, Schema.

